- b. Study duration and number of study visits required of research participants.

Participants will complete a Screening visit and will be enrolled in this study for a total of 5 days (Admission Day + 4 session days; Figure 1).

- c. Blinding, including justification for blinding or not blinding the trial, if applicable.

Participants will be informed in the consent will that the study drug may consist of one or more of numerous different drug classes (e.g., opioids, stimulants, over-the-counter medications). This is a common practice in laboratory-based studies of drug effects, a practice that we have followed for several years, and one that is recommended in peer-reviewed guidelines for abuse liability testing (103, 104). We will inform participants of the risks associated with hydromorphone (without revealing the drug type) in the consent form so they will be able to make an informed decision about study participation. Participants will receive double-blind oral doses of hydromorphone or placebo during the study to prevent expectancy effects and enable a rigorous evaluation of opioid administration on a variety of clinically-relevant outcome measures. Staff members will also be blinded to what study drug is being provided.

- d. Justification of why participants will not receive routine care or will have current therapy stopped.

N/A

- e. Justification for inclusion of a placebo or non-treatment group.

A placebo condition has been included as a comparison for opioid-induced effects.

- f. Definition of treatment failure or participant removal criteria.

Participants will be removed from study participation if they ask to be removed, if they exhibit an allergic reaction to the study drug, if they fail to comply with the requirements of the study, or if new information becomes available that suggests that continued study participation may put them at increased risk of adverse events.

- g. Description of what happens to participants receiving therapy when study ends or if a participant’s participation in the study ends prematurely.

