**Association Model:** Our primary goal is to demonstrate the impact of SNP variation across OPRM1 on variability in response to hydromorphone across time and dose. Association analyses will be performed by modeling genotype at each SNP in a general linear model. In its simplest form this test, commonly termed the measured genotype analysis (137), models the influence of genotypic variation at a given locus on variation in the quantitative trait, essentially a one-way Analysis of Variance (ANOVA). This approach provides a distinct advantage in that it can easily be extended to a two-way ANOVA to model genotype effects across 3 different doses of drug. In addition, the flexibility of the GLM allows incorporation of ancestry covariates and environmental moderators or mediators. We will examine the impact of OPRM1 at each time-point in separate analyses and account for the multiple testing using LD-adjusted Bonferroni correction (see below).

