**Power and Correction for Multiple Testing:** Power (1-Type II error) and correction for multiple testing (control of Type I error) are important considerations in any genetic association study. Typically investigators attempt to control the Type I error rate of a given set of hypothesis tests by controlling the family wise error rate through manipulation of the alpha level of the test. This is not problematic when a handful of tests are performed at an alpha level (false positive level) of 5%, where the usual approach is the Bonferroni correction. We anticipate performing tests across multiple time-points and must adjust our target alpha level. Importantly, our 71 selected SNPs across the OPRM1 gene (see below) do not represent 71 independent tests due to correlation between SNPs. We will use an approach, termed SNPSpD (138) which uses spectral decomposition to estimate the number of independent tests across the region. Using available HapMap data, we estimate 44 independent tests across the region. We calculate power for the GLM approach modeling the effect of genotype on phenotype. If we assume a constant effect size difference between genotype groups (at each dose other than placebo), at an alpha level conservatively adjusted for 50 tests to .001, using the entire completer sample (N= 100) or the sex subsamples (N=50), we have >80% power for modest effect sizes of ~.45 and .67 respectively. In our calculations, effect size (Cohen's d) is the mean difference between genotype groups in standard deviation units. Importantly, this effect size is well within the range seen by other studies examining drug response difference in OPRM1 (e.g., Ray et al., 2004: effect size = 1.2).

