**SNP selection (for association testing and control of Local Ancestry):** SNPs will be genotyped across the OPRM1 region to allow us to test associations across the gene and account for genetic ancestry (ethnicity). Typing all available SNP markers across the candidate gene set is inefficient and not necessary since many will provide redundant information due to linkage disequilibrium (LD). A more cost-effective strategy is to select a subset of representative SNPs (tagSNPs) that are in strong LD (measured through pairwise  $r^2$ ) with other SNPs that are therefore not required for genotyping in order to capture the haplotypic diversity across the gene. We followed this approach across OPRM1 with the Tagger algorithm at an  $r^2$  value of 0.8 and a minor allele threshold of 0.05 (139). We force included all predicted functional variation with allele frequency > .03 to allow for secondary hypothesis testing across OPRM1 functional SNPs. We used the latest Data release 21 (CEU Sample) of HapMap (<http://www.hapmap.org>) in conjunction with the NCBI build 35/hg17 of gene and EST data at UCSC Genome Browser (<http://genome.ucsc.edu/cgi-bin/hgGateway>). Using this approach, we selected 71 SNPs across the OPRM1 region for association testing and control of local ancestry. In our approach, we will re-estimate local ancestry for

each SNP association, dropping the tested SNP from ancestry estimation. Our approach to accounting for population stratification is detailed below.

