**Analysis of pain testing sessions:** We hypothesize that OPRM1 SNP variants will exhibit greater pressure pain thresholds, greater CPM efficiency, lower hydromorphone-related analgesia, and lower cortisol stress response than participants with the major allele, and that results will be positively correlated with response to self-report and physiologically-mediated hydromorphone drug effects collected during days 3-5. Pressure pain threshold will be estimated by averaging the results of the 2 administrations to radiobrachialis and quadriceps muscle groups. We will generate a CPM index for each participant [(mean pressure pain threshold during cold pressor)/(mean pressure pain threshold prior to cold pressor)] x 100 (90). These values will provide a quantitative measure of percent change in the test stimulus (i.e., pressure point threshold). Mixed effects regression models with a random intercept will be used to compare dependent variables (pressure pain threshold, DNIC threshold, DNIC index) as a function of within-subject drug effects (placebo vs. hydromorphone), and between-subject effects of OPRM1 SNP analysis will be conducted as specified in Aim 1. Gender, age, and race have been associated with response to pain and the CPM test (146-148). Gender will be evaluated using independent subgroup analyses and age and race will be included as covariates. Finally, subscale scores of self-report measures of pain and coping strategies will be compared between the two genotype groups using independent samples t-tests, and drug identification data will be compared using a chi-square for each drug condition. We expect that both experimental manipulations will induce pain in the minor and major allele groups, and that participants with the minor allele will demonstrate lower sensitivity to pain (e.g., greater pressure pain magnitudes), lower NRS ratings of pain, lower cortisol response to painful stimuli, and lower analgesic relief from hydromorphone compared to the major allele participants.

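### The >80% power claimed for d of about .45 (N=100) and .67 (N=50) at alpha .001 cannot be reproduced from the stated inputs and is far too high for the basic genotype test

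*Combined protocol and SAP*

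**What the plan says.** Section 7c, Power and Correction for Multiple Testing, sets the test level "at an alpha level conservatively adjusted for 50 tests to .001" and states that "we have >80% power for modest effect sizes of ~.45 and .67 respectively". The two figures belong to the full completer sample (N=100) and to each sex subsample (N=50). The paragraph defines the effect size, Cohen's d: it "is the mean difference between genotype groups in standard deviation units". It assumes the same genotype difference at every dose except placebo.

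Section 7c, Association Model, describes the test. Each SNP is entered in a general linear model, which in its simplest form is a one-way analysis of variance on genotype and can be extended to a two-way analysis over three doses. For time, the plan is explicit: "We will examine the impact of OPRM1 at each time-point in separate analyses".

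Section 7c, SNP selection, chooses tag SNPs with "a minor allele threshold of 0.05" and forces in predicted functional variants with frequency above .03, giving 71 SNPs. The power paragraph estimates that these amount to 44 independent tests.

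**The concern.** A between-person comparison of 50 against 50 cannot normally detect a difference of .45 SD with 80% power at alpha .001. The figure must therefore draw on something the paragraph leaves out: repeated doses, a placebo contrast, a particular genotype coding, or a different effect-size measure. Five inputs are missing: the tested term, the SD that standardises d, sidedness, the correlation between doses within a person, and the genotype split.

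This matters because the sentence is the only quantitative support for N=100 and for subsamples of 50, and Section 7c (Analysis of pain testing sessions) evaluates gender by independent subgroup analyses. Alpha .001 is set to cover all the selected SNPs, so a reader will take >80% power to hold across them. Someone relying on it could read a null result as evidence of no effect when the test had little chance of finding one.

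**Working it through.** **Inputs from Section 7c.** Alpha = .05/50 = .001, which is exact. N=100 with d=.45; N=50 with d=.67. The difference d is the same at each of three active doses and zero at placebo.

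**Assumptions, because the plan gives none.** Two-sided test; two genotype groups with carrier share p; SD 1 at every dose; equal correlation r between any two doses in the same person.

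**Formula.** Power is the probability that a noncentral F(1, N−2) with noncentrality λ = N·p(1−p)·d²/v exceeds the 99.9th percentile of central F (11.51 for N=100, 12.29 for N=50). Here v is the outcome variance:
- one dose: v = 1
- mean of three active doses: v = (1+2r)/3
- active mean minus placebo: v = (1+2r)/3 + 1 − 2r = 4(1−r)/3

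**1. Attempt to reproduce the plan's figure (one dose, equal groups).** λ = 100 × .25 × .45² = 5.06, giving 13.5%. λ = 50 × .25 × .67² = 5.61, giving 14.6%. One-sided, the figures are 18.5% and 20.1%. Even at an unadjusted two-sided .05 they are only 61% and 64%.

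**2. Using the doses (equal groups; N=100 / N=50).**

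| r | Mean of three active doses | Active mean minus placebo |
|---|---|---|
| 0 | 69% / 72% | – |
| .3 | 38% / 41% | – |
| .5 | 27% / 29% | 27% / 29% |
| .7 | 20% / 21% | 57% / 60% |
| .8 | – | 83% / 85% |

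The mean of active doses falls short of 80% even at correlation 0; a one-sided test there gives 76% / 79%. The placebo contrast reaches 80% at r = .79 / .78. With placebo as a covariate, v = (1+2r)/3 − r² with one fewer degree of freedom, and the requirement is r = .74 / .72.

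**3. Additive (per-allele) coding.** Replace p(1−p) by 2q(1−q), with q the allele frequency and d the effect per allele.
- Mean of three doses, r = .3: 83% / 85% at q = .5, but 7% / 8% at q = .05.
- Placebo contrast, r = .6: 83% / 85% at q = .5.
- Placebo contrast, r = .7: 88% / 90% at q = .3 and 73% / 76% at q = .2.
- Placebo contrast, r = .8: 93% / 95% at q = .2, but 25% / 27% at q = .05.

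**4. Rarer SNPs with carrier coding.** At minor allele frequency .05, Hardy-Weinberg proportions give 1 − .95² = 9.75% carriers, about 10 of 100 or 5 of 50. With p = .10, one dose gives 2.4% / 2.6%. The placebo contrast gives 5% / 5% at r = .5, 11% / 12% at r = .7 and 23% / 24% at r = .8. Reaching 80% needs r of about .92. At r = .8 the contrast needs a carrier share of at least 39% / 35%.

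**5. What the design can detect at 80% power.** The required λ is 18.06 (N=100) and 19.19 (N=50), so detectable d = √(λ·v/(N·p(1−p))).

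| Test | Equal groups, N=100 / 50 | 10% carriers, N=100 / 50 |
|---|---|---|
| One dose | .85 / 1.24 | 1.42 / 2.06 |
| Placebo contrast, r = .5 | .69 / 1.01 | 1.16 / 1.69 |
| Placebo contrast, r = .7 | .54 / .78 | .90 / 1.31 |
| Placebo contrast, r = .8 | .44 / .64 | .73 / 1.07 |

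Conversely, 80% power on one dose with equal groups needs a total of 343 people for d=.45 and 158 for d=.67.

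**6. Possible sources of the stated figures.** Two readings come close. Neither can be confirmed from the documents.
- A three-group analysis of variance at alpha .001 needs Cohen's f = .460 / .676 for 80% power, close to the stated values, so an f may have been labelled d. For two equal groups, f = .45 means d = 2 × .45 = .90.
- Treating three doses per person as 300 / 150 independent observations, one-sided, gives 78% / 83%. That ignores the within-person correlation.

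**The case against.** The strongest reply is that one dose is not what was powered. The paragraph assumes an effect at every active dose and none at placebo, which points to a repeated-dose calculation. Analysing time-points separately does not mean analysing doses separately. Section 4e also says "A placebo condition has been included as a comparison for opioid-induced effects", and the pain outcomes are to be analysed by mixed models of placebo against hydromorphone. The plan's one use of two-sample testing, "compared between the two genotype groups using independent samples t-tests", concerns questionnaire subscales, not the SNP tests. All of this stands: the stated power is unsupported, not impossible under every model. Additive coding with a placebo contrast also reaches 80% at correlations below .79 when alleles are common.

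Each such route still requires a contrast, coding, correlation and allele frequency that the plan does not state, and none of those examined extends to allele frequency .05. The carrier coding used for the 10% figures is likewise an assumption, but additive coding hardly improves matters there (25% / 27% at correlation .8).

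The plan also cites a reported effect of 1.2. At that size, one dose with N=100 has 99% power with equal groups and 92% with 20% carriers; N=50 has 76% and 47%. This tempers the consequence for common SNPs in the full sample. It does not rescue a claim made for .45 and .67, nor the sex subsamples.

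**Conclusion.** The point holds, and the paragraph needs correcting before anyone relies on it. The stated inputs do not yield >80% power. For the basic genotype test the figure is 13.5% and 14.6% in the best case of equal groups, and the detectable effects are nearly double those stated (.85 against .45, 1.24 against .67). On the more favourable multi-dose readings, 80% depends on an unstated combination of contrast, coding, high correlation or common alleles. At the plan's own allele-frequency threshold it would need a correlation of about .92 under carrier coding.

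These results assume two-sided alpha .001, equal correlation between doses, equal SDs and, for the carrier share, Hardy-Weinberg proportions. Every correlation is assumed, since the documents give none; the ranges above show how much the answer depends on it.

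**What to change.** Keep N=100 and rewrite the power paragraph for the test that will actually be run. State the tested term, the SD that standardises d, sidedness, the within-person correlation with a range, and the genotype coding and split.

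- **If the powered test is genotype on one dose**, suitable wording is: *At two-sided alpha .001 there is 80% power to detect d = 0.85 (N=100) or 1.24 (N=50) with equal genotype groups, and d = 1.42 or 2.06 with 10% minor-allele carriers.*
- **If it is the active-minus-placebo contrast**, justify the correlation and report the detectable d at .5, .7 and .8 for equal groups and for 10% carriers, as in the last table of the working.
- **If it is an additive model**, say that d is per allele and give power by allele frequency, including .05.
- **If the figures were Cohen's f**, say so. For two groups convert with d = f/√(p(1−p)), which is 2f only when the groups are equal. For three groups, state the genotype frequencies and the pattern of means instead.

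Drop the word *modest* unless the recalculated value supports it. The cost is one rewritten paragraph with less favourable figures; no participants are added and no procedure changes.

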## 7. Study Statistics

a. Primary outcome variables. The primary outcome variables are self-reported ratings of drug high and liking, changes in pupil diameter and blood pressure, pain threshold on 2 laboratory measures of pain, and analgesic efficacy in response to laboratory-induced pain. We expect that individuals with the minor allele of the A118G SNP and other

tagging SNPs across the OPRM1 gene will find hydromorphone more reinforcing (e.g., higher self-report ratings of high and drug-liking) and exhibit greater opioid-induced physiological changes (e.g., pupil diameter, blood pressure). Research also suggests the OPRM1 gene may also confer greater sensitivity to the negative effects of opioids, which may be observed as measuring greater ratings of nausea. We also hypothesize the minor allele and other tagging SNPs across the OPRM1 gene will produce higher pain threshold on 2 laboratory measures of pain, and lower analgesic efficacy in response to laboratory induced pain.

**b. Secondary outcome variables.** Decreases in cortisol levels as a function of the degree of pleasant effects of hydromorphone and painful stimuli, delay-discounting curves, and the effect of sex on all outcome measures. We hypothesize that individuals with the minor alleles will have greater decreases in cortisol levels as a function of the degree of pleasant effects of hydromorphone, lower cortisol in response to painful stimuli, and steeper discounting curves on a delay-discounting task. Finally, although we expect that the A118G will be associated with these effects, we hypothesize that several of the additional OPRM1 tagging SNPs will contribute to effect magnitude.

**c. Statistical plan including sample size justification and interim data analysis:** The aims of the proposed study will explore the impact of genetic variation across the OPRM1 gene on hydromorphone response. There are specific steps we describe below to assure that we interrogate all known functional variation across the OPRM1 gene, adequately cover all other variation using appropriately selected tagging SNPs, prevent spurious associations due to population stratification by accounting for local ancestry, and properly control the Type I error rate.

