**Population Stratification:** In the context of genetic association testing, population stratification refers to genetic differences between subpopulations. This is especially problematic in instances where the investigators are blind to the presence of stratification and/or the population substrata also differ phenotypically. In these cases, association analyses will be prone to generate spurious genotype-phenotype relationships. Previously, several methods, including genomic control (140) and STRUCTURE (141) were proposed to deal with this issue by either correcting the test statistic for the average level of stratification or a priori grouping of population subsets. At the onset of the GWAS era, the wealth of genome-wide data gave rise to additional approaches which rely on the correlation structure of genetic information to identify cryptic population structure. EIGENSTRAT (142) is an example of an approach that uses genomewide data to infer principal components of population membership. Recently, several investigators (143, 144) have noted that differences in global (genomewide) versus local (at a gene or LD block) ancestry exist, especially in admixed populations (e.g., African-American). This is particularly germane to our setting given: 1) the genetic ancestry of the ECA sample is a mix of European-Americans and African-Americans, 2) the focus on a relatively small number of genes, and 3) the lack of genome-wide SNP data. We will use an approach (WinPOP/LAMP; (144, 145) to estimate proportions of local ancestry at each tested gene and account for stratification based on those mixing proportions in subsequent GLM tests. In order to accomplish this we will densely tag OPRM1.

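### The pain and coping subscale t-tests and the drug-identification chi-squares carry no race or ancestry adjustment; Aim 1 is better protected, but by a one-gene ancestry estimate of unstated accuracy

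*Combined protocol and SAP*

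**What the plan says.** All of this is in section 7c of the combined protocol and SAP.

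- **Purpose.** The statistical plan opens with the aim to "prevent spurious associations due to population stratification by accounting for local ancestry".
- **Aim 1 adjustment** (Population Stratification). The sample is described as mixed European-American and African-American, without genome-wide SNP data. The software is used "to estimate proportions of local ancestry at each tested gene and account for stratification based on those mixing proportions in subsequent GLM tests". No race or genome-wide ancestry term is named.
- **Source of the estimate** (SNP selection). "we selected 71 SNPs across the OPRM1 region for association testing and control of local ancestry". On how these tags were chosen: "We used the latest Data release 21 (CEU Sample) of HapMap".
- **Safeguard** (SNP selection, one sentence split by a page break). "In our approach, we will re-estimate local ancestry for" "each SNP association, dropping the tested SNP from ancestry estimation".
- **Pain models** (Analysis of pain testing sessions). The plan says gender, age and race have been linked to pain response and the CPM test, then: "Gender will be evaluated using independent subgroup analyses and age and race will be included as covariates". The SNP effects are to be handled as in Aim 1.
- **Subscales and drug identification** (same paragraph). Pain and coping subscale scores are "compared between the two genotype groups using independent samples t-tests", and drug identification is compared by a chi-square within each drug condition. No covariate is mentioned for either.

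**The concern.** Genotype is not randomised. A comparison by genotype is therefore also, in part, a comparison by ancestry whenever the allele is commoner in one ancestry group. If the outcome differs between those groups for any other reason, the difference appears as a genotype effect. The plan recognises this risk and gives it a paragraph.

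The subscale and drug-identification tests nevertheless have no protection, and they sit in the paragraph that calls race relevant to pain and adjusts for it in the pain models. At stake is a set of genotype differences in pain and coping scores that could be ancestry differences.

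The question for Aim 1 is narrower. Its models do carry local ancestry, but the estimate comes from one gene, using tags picked for linkage disequilibrium in a European panel, and the plan says nothing about how accurate it will be.

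**Working it through.** **Plan figures.** The plan gives no error rate on this point to reproduce. It does give N = 100 completers and a per-test alpha of .05/50 = .001, which is correct.

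**Assumed inputs, not in the documents.** Two equal groups of 50, one European and one admixed with 20% European ancestry. Allele frequencies (European v African source) of .15 v .03 or .40 v .10. No genotype effect. A group difference in outcome of d = 0.5 or 0.8 within-group SD. Genotype coded as carrier or non-carrier, as a two-group t-test requires.

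**Step 1: the unadjusted test by hand.** Bias = d × (European share among carriers − European share among non-carriers). Rejection rate at .05 ≈ P(Z > 1.96 − λ) + P(Z < −1.96 − λ), where λ = bias/SE.

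*Upper case, .40 v .10, d = 0.8*
- European carriers: 1 − .60² = .640. Admixed allele frequency: .2 × .40 + .8 × .10 = .16. Admixed carriers: 1 − .84² = .294.
- European share: .640/(.640 + .294) = .685 of carriers and .360/(.360 + .706) = .338 of non-carriers.
- Bias = .8 × .347 = .278 SD.
- About 46.7 carriers and 53.3 non-carriers. SD within genotype group ≈ 1.068. SE = 1.068 × √(1/46.7 + 1/53.3) = .214.
- λ = 1.30, so the rejection rate is about .25.

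*Lower case, .15 v .03, d = 0.5*
- European carriers: 1 − .85² = .278. Admixed allele frequency: .054. Admixed carriers: 1 − .946² = .105.
- European share: .725 of carriers and .447 of non-carriers. Bias = .5 × .279 = .139 SD.
- About 19.1 carriers and 80.9 non-carriers. SE ≈ .262.
- λ = .53, so the rejection rate is about .08.

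Coding by allele count instead of carrier status raises the upper case to about .27. Hence the range of about 8% to 27%.

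**Step 2: simulation with local ancestry in the model.** Each haplotype's ancestry is drawn, and the allele is drawn given that ancestry. The ancestry call is informative with the stated probability and otherwise random. There were 4,000 runs per scenario, so simulation error near .05 is about 1.96 × √(.05 × .95/4000) = .007. Rejection rates at nominal .05:

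| d (SD) | Allele frequencies | Unadjusted | Local ancestry exact | 80% informative | 60% informative | Race in model |
|---|---|---|---|---|---|---|
| 0 | .15/.03 | .054 | .052 | .053 | .051 | .052 |
| 0 | .40/.10 | .048 | .054 | .057 | .051 | .051 |
| 0.5 | .15/.03 | .078 | .046 | .050 | .056 | .045 |
| 0.5 | .40/.10 | .133 | .058 | .055 | .075 | .058 |
| 0.8 | .15/.03 | .131 | .053 | .060 | .075 | .053 |
| 0.8 | .40/.10 | .246 | .053 | .066 | .096 | .054 |

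The unadjusted column agrees with the hand calculation. The worst case in the table (last row) at nominal .001 is .021 unadjusted and .0045 with 60% informative calls. At 50% informative calls the same case reaches about .14 at nominal .05 and .008 at nominal .001.

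**Step 3: why exact local ancestry suffices.** In a two-source admixed sample, genotype at a locus depends on overall ancestry only through ancestry at that locus. Once that is in the model, genotype and overall ancestry are independent, and the outcome's dependence on overall ancestry cannot reach the genotype coefficient. The exact column shows this. Residual confounding therefore needs error in the local estimate, or structure beyond two source populations.

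**The case against.** The plan takes stratification seriously. It re-estimates ancestry for every SNP with that SNP left out, tags the gene densely for the purpose, and says its GLM can take ancestry covariates. Section 4 (Genetic Analysis) also mentions ancestral markers. The subscale questionnaires are listed among measures that establish eligibility and characterise the sample, and neither they nor drug identification is a primary or secondary outcome. The documents link race to pain response, not to high, liking, pupil diameter or blood pressure, and confounding needs such a link. The sample described as mixed is called the ECA sample, a term not defined elsewhere, so even this trial's ancestry mix is uncertain.

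Most of this stands, and it limits the point. It does not remove it. The GLM wording is permissive and names no race or global term. The ancestral markers are referred to the statistical section, which describes none outside OPRM1. Leaving out the tested SNP does not show that an estimate from its neighbours is accurate. Nothing in the plan protects the t-tests or chi-squares.

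A reader might infer that the Aim 1 results are confounded because one-gene ancestry must be noisy. The documents do not support that: they give no accuracy figure, and an accurate estimate would leave no two-way admixture confounding. Error rates as high as .024 at nominal .001, or 42% unadjusted at nominal .05, arise only if the two groups are taken as unadmixed and, for the first figure, if the covariate is a noisy proxy for group membership. That is not the planned method.

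**Conclusion.** The gap is clear for the subscale t-tests and drug-identification chi-squares, which are unadjusted in a paragraph that treats race as relevant to pain. For the t-tests, false-positive error would be about 8% to 27% at nominal .05 under the stated assumptions, and nominal if scores do not differ by ancestry. The chi-squares share the exposure, though the simulation used a continuous outcome and does not size it for them. These are supportive comparisons, so a reader should not infer that the primary conclusions carry error of this size.

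For Aim 1 the risk is conditional. It is nil with accurate local ancestry and small at 80% informative calls (at most .066 at nominal .05). At 50% it reaches about .14, or eight times the nominal .001, in the most adverse case tried. Which of these applies cannot be told from the documents.

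The simulation cannot show that self-reported race would remove all residual confounding. The outcome was made to differ by group, so adjusting for group is complete by construction.

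**What to change.** - Replace the subscale t-tests with linear regressions, and the drug-identification chi-squares with logistic regressions within each drug condition. Both should carry local ancestry, race, age and sex.
- Add race and age, already covariates in the pain models, beside local ancestry in the Aim 1 GLMs. Report Aim 1 results with and without race.
- State whether the ancestral markers in section 4 lie outside OPRM1 and, if so, how they enter the models.

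The cost is SAP wording and a few degrees of freedom out of 100 completers, somewhat more noticeable in the sex subsamples of 50. No new data are needed, since the pain models already require race. One limit remains: self-reported race does not capture variation in admixture within a group, so it supplements local ancestry and does not replace it.
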